## 9.3 POPULATIONS FOR ANALYSES

All participants will be included in all analyses because we are using a within-participant design.

## 9.4 STATISTICAL ANALYSES

### 9.4.1 GENERAL APPROACH

There are no categorical outcomes. Key measures are all continuous outcomes, and are described in detail in the next section. They will be analyzed according to pre- versus post-stimulation means and also in sham versus active stimulation. We will also report standard errors for each outcome. Key outcomes have multiple associated measures. Multiple measures will be used to assess reliability by parallel forms.

We will use standard frequentist cut-offs of  $p < 0.05$  for all statistical tests, correcting for multiple comparisons. Key t-tests will include pre-post and sham-versus-active distinctions in E/I balance measures, oculomotor control task performance measures, and measures of criticality.

Covariates of no interest to be included are sex and age which we will incorporate via multiple regression to ask whether rTMS alters key outcomes (described in the next session).

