### 9.4.2 ANALYSIS OF THE PRIMARY ENDPOINT(S)

The following key outcomes will be assessed in this study. All measures are interval with the exception of the categorical covariate of sex.

- Subjective effort
  - Likert scale ratings (ranging from 1-10) of task-induced effort, demand, time pressure, and stress
  - subjective values as estimated from an indifference point discounting procedure
  - self-reported motivation to engage in demanding tasks on a set of Likert scales with continuous values ranging from 0-20
  - Pupil dilation as a continuous variable which has been shown to index the cognitive and physical effort associated with oculomotor tasks (Koevoet et al., 2024)
- E/I balance
  - fEI derived measure with exponents ranging approximately from 0.0-2.0
  - avalanche branching statistics with values approximately from 0.5 to 1.5
  - power-law exponents with exponents approximating -2.0
- Critical dynamics
  - Long range temporal correlations – a derived measure with exponents ranging approximately from 0.5-1.0
  - Avalanche size and duration distribution exponents approximating -2.0 and -1.5, respectively.

- Band-limited bistability with values ranging from 0.0 to ~5.0
- Memory guided saccade task performance
  - overall accuracy as degrees of visual angle
  - median reaction times in terms of time from cue until a saccade is launched
  - trial-wise variability in accuracy (SD)
  - trial-wise variability in reaction time (SD)
- Anti-saccade task performance
  - Overall accuracy rate as a percent of trials with correct anti-saccade versus incorrect pro-saccade
  - Median reaction times in terms of time from cue until a saccade is launched
  - trial-wise variability in accuracy (SD)
  - trial-wise variability in reaction time (SD)

Primary analyses of these outcomes will entail multiple regression models in which outcomes will be regressed on cTBS condition (target versus sham), controlling for sex and age.

We will also test for inter-correlations among the primary endpoint measures. Namely, these correlations will test whether the degree to which rTMS alters one measure (e.g. functional E/I balance) correlates with stimulation effects on other measures (e.g. endpoint variability on the memory-guided saccade task).

We will use Pearson's correlations for all tests since our outcome measures are continuous, interval measures.

---

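### Section 9.4.1 calls agreement between different measures parallel-forms reliability; it is convergent validity and does not estimate measurement error

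*Protocol*

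**What the plan says.** Section 9.4.1 (General Approach) states: "Key outcomes have multiple associated measures". The next sentence is: "Multiple measures will be used to assess reliability by parallel forms". Read together, the forms are the measures grouped under each key outcome in section 9.4.2. Among them are:

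- **Memory-guided saccades:** "overall accuracy as degrees of visual angle", "median reaction times in terms of time from cue until a saccade is launched", and the trial-wise SD of each.
- **Subjective effort:** 1-10 ratings, discounting values, pupil dilation, and "self-reported motivation to engage in demanding tasks on a set of Likert scales with continuous values ranging from 0-20".
- **E/I balance:** "fEI derived measure with exponents ranging approximately from 0.0-2.0", "avalanche branching statistics with values approximately from 0.5 to 1.5" and "power-law exponents with exponents approximating -2.0".

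The protocol describes no alternate version of any task or scale and names no other reliability method. Section 9 says that no formal statistical analysis plan will be written, so the protocol does not leave this to a later document.

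**The concern.** Parallel-forms reliability is the correlation between two versions of one instrument that share the same true score and have equal error variance. Only then does the correlation equal the share of variance that is not error. When the measures are different quantities, their correlation also depends on how the underlying constructs relate and on any arithmetic link between the scores. It may be low when both measures are precise, or high when both are noisy.

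What is at stake is interpretation. Section 9.1 predicts individual-difference correlations between the effects of stimulation on E/I balance, criticality and effort, and section 9.4.2 plans Pearson correlations between stimulation effects on different measures. Measurement error attenuates such correlations. A reader who took the parallel-forms figure as reliability would misjudge by how much.

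**Working it through.** The protocol states no reliability figure, so there is none to reproduce. The check compares the named method with the listed measures and works through what the coefficient would show.

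**1. Do the measures meet the definition?** Within E/I balance, one measure runs from about 0 to 2, one from about 0.5 to 1.5, and one lies near -2.0. Within memory-guided saccades, one is an angle, one is a time, and two are within-person SDs. Equal true scores and equal error variances cannot hold across them.

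**2. What would the correlation between two measures estimate?** With independent errors, r(observed) = r(true) × √(rel₁ × rel₂). Assume both reliabilities are 0.7, so the root is 0.7:

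| Assumed true correlation | Expected observed correlation |
|---|---|
| 0.3 | 0.3 × 0.7 = 0.21 |
| 0.5 | 0.5 × 0.7 = 0.35 |
| 0.7 | 0.7 × 0.7 = 0.49 |
| 1.0 | 0.70 |

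Only the last row returns the reliability, and it requires that the two measures share one true score.

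**3. Illustration of an arithmetic link.** Section 9.4.2 defines anti-saccade accuracy as the percentage of correct trials and also lists its trial-wise SD. If trials are scored correct or incorrect, that SD is √(p(1 − p)), a function of accuracy p itself. With no measurement error and p spread evenly over an assumed range:

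| Assumed range of p | Correlation of p with its SD |
|---|---|
| 0.60-0.95 | -0.97 |
| 0.40-0.90 | -0.90 |
| 0.30-0.90 | -0.78 |
| 0.30-0.70 | 0.00 |

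In the opposite case, give every participant a true accuracy of 0.80, so that all differences are noise and reliability is 0. The correlation is -0.97 with 40 trials and -0.99 with 200 (assumed trial counts). For high accuracy the coefficient is therefore much the same whether reliability is 0 or 1. The protocol gives neither the accuracy range nor the trial count.

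**4. Which reliability matters for the planned correlations?** They relate change to change. For a simple difference with equal variances and equal level reliability, rel(change) = (rel − r) / (1 − r), where r = rel × true pre-post correlation. Assume level reliability 0.8:

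| Assumed true pre-post correlation | r | rel(change) |
|---|---|---|
| 0.5 | 0.40 | 0.40 / 0.60 = 0.67 |
| 0.7 | 0.56 | 0.24 / 0.44 = 0.55 |
| 0.9 | 0.72 | 0.08 / 0.28 = 0.29 |

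Good reliability of levels can thus go with poor reliability of change. For scale, with 60 participants (section 9.2) and two-sided 0.05, the smallest correlation detectable with 80% power is tanh((1.96 + 0.84) / √57) ≈ 0.35 on the observed scale. If both change scores had reliability 0.29, even a true correlation of 1 would appear as about 0.29.

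**5. Can the design give a proper estimate?** There are three stimulation sessions (section 4.1), EEG throughout each (section 8.1), and pre-stimulation rest as a comparator (section 9.1). For an assumed one-way ICC of 0.7 with 60 participants and three occasions, F = (1 + 2 × 0.7) / (1 − 0.7) = 8, and the 95% CI is 0.58 to 0.80. An assumed ICC of 0.5 gives 0.35 to 0.64, and 0.9 gives 0.85 to 0.94. The trial-wise SDs in section 9.4.2 show that trial-level task data will exist.

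**The case against.** The strongest reply is that nothing in the trial rests on this coefficient. Section 9.4.1 says only that reliability will be assessed. It does not say that the figure will correct correlations for attenuation or select endpoints. The regressions in section 9.4.2 do not use it, and the sample size in section 9.2 rests on meta-analytic effect sizes. This stands and keeps the point minor.

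The sentence may also be a loose way of saying that several indices of one construct will be checked for agreement. That reading is possible, and it leads to the same correction: such a check is convergent validity and should be called that.

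The accuracy example is a chosen pair. The protocol never says that accuracy will be correlated with its own SD as a reliability estimate, and the result moves from -0.97 to 0.00 with the assumed range. It illustrates the mechanism and does not predict a result.

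The remedy has limits too. Three baseline recordings are inferred from three sessions plus a pre-stimulation comparator; the schedule in section 1.3 does not list them separately. Its visit windows are wide (±50 to ±52 days), so a test-retest ICC would include real change between visits. Trial counts and recording lengths are not given.

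A reader might infer that the planned figure would be meaningless, or that it would undermine the trial's conclusions. The documents support neither. Agreement between indices is informative under its proper name, and the stimulation contrasts do not depend on it.

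**Conclusion.** The point holds as a minor correction. Section 9.4.1 names a method that the measures in section 9.4.2 cannot support: they are not parallel forms, and their correlations do not estimate reliability. This follows from the listed measures and needs no assumed number. The sizes shown (0.21 to 0.49 against a reliability of 0.7; -0.97 to 0.00 for the accuracy example; change-score reliability of 0.29 to 0.67) rest on assumed reliabilities, true correlations and accuracy ranges that the protocol does not give. The practical consequence is confined to reading the individual-difference correlations in sections 9.1 and 9.4.2.

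**What to change.** Replace the sentence in section 9.4.1 with three statements:

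- **(a) Internal reliability.** Odd-even split-half reliability with Spearman-Brown correction for the trial-based task measures, and split-segment reliability for the EEG measures where recording length allows. Compute each for single-session levels and for the change scores (post minus pre, active minus sham) that enter the correlations.
- **(b) Test-retest reliability.** An ICC with 95% CI for the EEG measures over the pre-stimulation recordings of the three stimulation sessions, noting that it includes real change over the variable interval between visits.
- **(c) Agreement between different measures of one outcome.** Report it only as convergent validity.

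The cost is a revised sentence and a little extra analysis of data already planned. No visit, measurement or sample-size change is needed.

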## 1 PROTOCOL SUMMARY

### 1.1 SYNOPSIS

Title:	Theta-burst stimulation modulates criticality and cognitive control
Grant Number:	R00MH125021
Study Description:	In this study we test the hypotheses that critical brain dynamics depend on the balance of cortical excitation to inhibition and that sub-criticality impacts on subjective cognitive effort and cognitive control.
Objectives*:	Primary Objective: Test whether continuous and intermittent theta burst stimulation can alter critical dynamics, cognitive control, and cognitive effort relative to sham stimulation. Secondary Objectives: Test whether the effects of continuous and intermittent theta burst stimulation reflect alterations in the cortical excitation to inhibition balance.
Endpoints*:	Primary Endpoint: Long-range temporal correlations and avalanche branching statistics from EEG signals. Cognitive control performance. Cognitive effort discounting of rewards. Secondary Endpoints: N/A
Study Population:	We will recruit 60 healthy young adults (30 F and 30 M; all 18-45 years old), from the Rutgers University Community in New Brunswick and Piscataway, NJ.
Phase* or Stage:	N/A
Description of Sites/Facilities Enrolling Participants:	This single-site study will be conducted at Rutgers University in the Center for Advanced Human Brain Imaging Research. No research will be conducted overseas.
Description of Study Intervention/Experimental Manipulation:	The study will involve three sessions of within-subject, crossover, double-blind, sham-controlled continuous and intermittent theta burst stimulation delivered either at the right frontal eye field.
Study Duration*:	24 months
Participant Duration:	Participants will complete all components within 4 months of their first visit.

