### 3 OBJECTIVES AND ENDPOINTS

OBJECTIVES	ENDPOINTS	JUSTIFICATION FOR ENDPOINTS	PUTATIVE MECHANISMS OF ACTION
Primary			
Test whether theta-burst stimulation induces a shift towards super- (intermittent theta-burst stimulation, or iTBS) or sub-critical dynamics (continuous theta burst stimulation, or cTBS) in the cortex during rest.	Diminished markers of critical dynamics including reduced long-range temporal correlations measured by detrended fluctuation analysis, and super-critical and sub-critical avalanche branching ratios.	Long-range temporal correlations ( $< 1.0$ ) and avalanche branching dynamics are widely used metrics of distance from the critical point (degree of sub-: $< 1.0$ and super-criticality $> 1.0$ ) in EEG studies.	Long-range temporal correlations and avalanche branching ratios of 1.0 are emergent properties of dynamical systems at a critical point. By reducing and increasing the E/I balance, theta burst stimulation should make the brain more sub-critical and super-critical, respectively, thus dampening these

OBJECTIVES	ENDPOINTS	JUSTIFICATION FOR ENDPOINTS	PUTATIVE MECHANISMS OF ACTION
			emergent properties.
Test whether theta-burst stimulation to the frontal eye fields (FEF) alters cognitive control relative to sham stimulation.	Increases or decreases in accuracy in the anti-saccade task	Criticality affords the capacity for inter-regional communication in the service of, e.g., top-down control from FEF to saccade motor regions. Thus, people with brains operating closer to criticality should show greater accuracy on the anti-saccade task. If cTBS makes brains more sub-critical, they should show less anti-saccade accuracy. If iTBS makes brains more critical (or even super-critical) during tasks, then it should increase anti-saccade accuracy relative to sham stimulation.	A decrease in the E/I balance in the FEF following cTBS or an increase in E/I balance following iTBS should make brains more sub-critical or more super-critical, respectively, thus decreasing and increasing the capacity for top-down anti-saccade inhibition, respectively.

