## 6 STUDY INTERVENTION(S) OR EXPERIMENTAL MANIPULATION(S)

### 6.1 STUDY INTERVENTION(S) OR EXPERIMENTAL MANIPULATION(S) ADMINISTRATION

#### 6.1.1 STUDY INTERVENTION OR EXPERIMENTAL MANIPULATION DESCRIPTION

The study intervention is modulation of cortical excitation to inhibition (E/I) balance in the right frontal eye field (FEF) by means of 2 trains of spaced continuous theta burst stimulation (cTBS) or intermittent theta burst stimulation (iTBS) using a transcranial magnetic stimulation device. As prior work (Huang et al 2005; Chung et al. 2018) has shown that cTBS reliably decreases the cortical E/I ratio with diverse cortical targets and iTBS increases the E/I ratio, we expect to replicate a reduction in E/I balance when cTBS is applied to the FEF and an increase in E/I balance when iTBS is applied. The mechanism of action is thought to be a manipulation of inhibitory neurotransmission across diverse timescales. The endpoint of this stimulation will be a modulation of the local E/I ratio that should last at least 60 minutes post-stimulation (Chung et al., 2016).

We will assess the changes in E/I balance by quantifying the functional E/I ratio as previously done in a study of the GABA receptor agonist Zolpidem (Bruining et al. 2020). We furthermore anticipate that a reduction in FEF E/I balance will also make the dynamics of FEF more sub-critical while an increase would make FEF more super-critical (Pfeffer et al. 2018; Poil et al. 2012). Thus, depending on whether participants' brains operate in a sub- or super-critical regime at baseline, we predict that cTBS and iTBS manipulations will either make their brains operate closer to or farther from criticality. If cTBS / iTBS make participants' brains operate closer to criticality, this will be reflected by an inferred functional E/I ratio of 1.0, and stronger long range temporal correlations. Conversely values farther from 1.0 will correspond with weaker long-range temporal correlations otherwise found in the brain in a critical state. Moreover, we will test the prediction that cTBS / iTBS to the FEF will affect oculomotor control. Specifically, we predict that since criticality affords maximal susceptibility and flexibility, tasks which require more stability (e.g. short term memory tasks) will be performed with less precision and more trial-to-trial variability in accuracy and reaction times at criticality. Since criticality also maximizes information transfer capacity,

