### 9.1 STATISTICAL HYPOTHESES

- Primary Endpoint(s):

We predict that, relative to pre-stimulation rest, continuous theta burst stimulation (cTBS) will result in a reduction of the local balance of cortical excitation to inhibition as reflected in the functional E/I balance in proximity to stimulated targets. Conversely, we predict that intermittent theta burst stimulation (iTBS) will result in an increase of the local balance of cortical excitation to inhibition as reflected in the functional E/I balance in proximity to stimulated targets. We also predict these changes to exceed any effects of sham stimulation, and thus another set of endpoints will compare the functional E/I balance after sham versus either active stimulation protocol.

We also predict that, relative to pre-stimulation rest, cTBS and iTBS protocols that will either reduce or strengthen markers of critical dynamics (including, e.g., long-range temporal correlations) in proximity to stimulation targets. The direction of the effect will depend on how the brain operates at baseline. For example a brain that operates in a more sub-critical (lower E/I balance) regime will show an increase in long-range temporal correlations following iTBS (because it should raise the functional E/I balance).

We also predict that, relative to sham stimulation, cTBS and iTBS will alter oculomotor task performance. Specifically, because criticality makes brains more flexible and susceptible, protocols which make brains operate closer to criticality will cause performance to become more variable and worse on the memory-guided saccade task which depends on stability of short-term memory representations. Also, because criticality increases information transfer capacity between brain regions, protocols which make brains operate closer to criticality will cause performance to become better on the anti-saccade task which depends on robust top-down communication of control signals to override bottom-up reflexive saccades to the target.

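### Criticality markers: the comparator is sham in the synopsis but only pre-stimulation rest in 9.1; uncontrolled pre-post t-tests are left unranked, and no stated model carries the baseline dependence that 9.1 predicts

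*Protocol*

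**What the plan says.** **Comparator.** The synopsis asks whether the two stimulation protocols "can alter critical dynamics, cognitive control, and cognitive effort relative to sham stimulation". Section 9.1 words the corresponding hypothesis differently: "We also predict that, relative to pre-stimulation rest, cTBS and iTBS protocols that will either reduce or strengthen markers of critical dynamics". That paragraph has no sham clause. The functional E/I paragraph just before it does: "We also predict these changes to exceed any effects of sham stimulation". The oculomotor and effort predictions in 9.1 are both set against sham. In Section 3 the first primary objective begins "Test whether theta-burst stimulation induces a shift towards super- (intermittent theta-burst stimulation, or iTBS) or sub-critical dynamics" and names no comparator in its objective or endpoint column. Each of the other three primary objectives refers to sham in one of those columns.

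**Tests.** Section 9.4.1 says: "Key t-tests will include pre-post and sham-versus-active distinctions in E/I balance measures, oculomotor control task performance measures, and measures of criticality". The text before it lists pre versus post and sham versus active as two separate comparisons, and asks for correction for multiple comparisons. Section 9.4.2 says: "Primary analyses of these outcomes will entail multiple regression models in which outcomes will be regressed on cTBS condition (target versus sham", with sex and age as covariates. Section 4.1 adds session order.

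**Direction.** Section 9.1 says of the criticality markers: "The direction of the effect will depend on how the brain operates at baseline". Section 6.1.1 likewise makes closeness to criticality turn on whether "brains operate in a sub- or super-critical regime at baseline". The endpoint column of the first row in Section 3 predicts reduced long-range temporal correlations with no such condition.

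Section 9 states that no formal SAP will be written, so these sections carry the plan.

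**The concern.** There are two separate problems.

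First, a within-session pre-post change mixes any stimulation effect with whatever else changes over a session, such as drowsiness or electrode drift. The sham session exists to remove that. The hypothesis for the trial's leading outcome is nevertheless worded so that a pre-post change would satisfy it. 9.4.1 gives the test of that change the same key status as the controlled one, and no sentence says that a pre-post result alone cannot support a stimulation claim. For iTBS the gap is wider: the primary regression names only the cTBS condition, so its specified sham-controlled test is the t-test in 9.4.1.

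Second, if stimulation moves some participants towards criticality and others away from it, a marker that measures distance from criticality rises in some and falls in others. A contrast averaged over participants then estimates something near zero even if the hypothesis is true. The stated covariates (sex, age, session order) do not separate the two groups.

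**Working it through.** **1. The plan's own figure.** Section 9.2 gives n = 60, g = 0.21 in absolute value for late iTBS, and 36% power. For a paired t-test, noncentrality λ = g√n = 0.21 × √60 = 1.627 with 59 df. Two-sided 0.05 gives 36.0%, so the stated power is that of one paired contrast. No figure in 9.2 is disputed here.

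**2. Pre-post test under non-specific change.** Assumption, not in the protocol: no stimulation effect, and a change δ of 0.1, 0.2 or 0.3 SD of the pre-post change, equal under active and sham. Then λ = δ√60 = 0.775, 1.549 or 2.324, and the rejection rate is P(|T| > critical value) for noncentral t with 59 df.

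| Two-sided level | Critical t | δ = 0.1 | δ = 0.2 | δ = 0.3 |
|---|---|---|---|---|
| 0.05, uncorrected | 2.001 | 11.9% | 33.2% | 62.8% |
| 0.05/6 | 2.730 | 3.0% | 12.8% | 35.1% |
| 0.05/36 | 3.356 | 0.7% | 4.3% | 16.5% |

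Six is the number of EEG bullets in 9.4.2 (three under E/I balance, three under critical dynamics). Thirty-six is all 18 bulleted measures times two protocols. The protocol names no correction method; Bonferroni is assumed.

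**3. Sham contrast under the same change.** The change cancels: (μ + δ) − (μ + δ) = 0. In simulation (20,000 runs) the contrast of post-stimulation values rejected in 5.1/4.6/5.0% at uncorrected 0.05. If the pre-post and sham tests must both be significant in the same direction, the rate is 0.9/1.5/2.0%. Inflation therefore needs a pre-post result claimed alone.

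**4. Which markers can cancel.** Section 3 predicts branching ratios below 1.0 after cTBS and above 1.0 after iTBS. This is one direction per protocol, so a signed measure need not cancel. In 6.1.1 long-range temporal correlations are stronger nearer criticality, so their direction depends on the starting point.

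**5. Size of the cancellation.** Assumptions: effect +d in the sub-critical share π and −d in the rest; between-person SD 1; session deviations SD 1 with pre-post correlation 0.5; contrast adjusted for the pre-stimulation value.

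- Mean effect = (2π − 1)d. For d = 0.5 this is 0 at π = 0.5 and 0.2 at π = 0.7.
- Variance of the adjusted difference = 2(1 − 0.5²) + 4π(1 − π)d². At π = 0.7 this is 1.5 + 0.84 × 0.25 = 1.71.
- λ = 0.2/√(1.71/60) = 1.18, which gives power of about 21%. At π = 0.5 power is the 5% test level.

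For a condition-by-baseline term, functional E/I is assumed to be measured before stimulation in three sessions (reliability 0.5 each, averaged) and independent of the marker. Simulated power at uncorrected 0.05:

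| d | Sub-critical share | Average contrast | Condition-by-baseline term |
|---|---|---|---|
| 0.5 | 50% | 5% | 53% |
| 0.5 | 70% | 21% | 42–43% |
| 0.8 | 50% | 5% | 88% |
| 0.8 | 70% | 40% | 77% |

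With no effect the term rejected in 4.8% to 5.2% at every drift from 0 to 0.3.

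**6. The same term after correction.** Take six tests: three critical-dynamics bullets times two protocols, critical t = 2.733 on 57 df. Power of 53% at 0.05 corresponds to λ of about 2.06, which gives about 26% at 0.05/6. Power of 42% corresponds to λ of about 1.79, which gives about 18%. At d = 0.8 the corrected figures are about 67% and 51%. On the same footing the average contrast at d = 0.5 and π = 0.7 (λ = 1.18) falls to about 7%.

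**The case against.** The strongest reply is that the sham comparison is already there. 9.4.2 lists critical dynamics among the outcomes of the target-versus-sham regression, 9.4.1 makes sham-versus-active a key test for measures of criticality, 6.1.1 promises to contrast both active protocols with sham, and 9.4.8 tabulates pre and post values for both conditions. All of this stands. A reader might infer from 9.1 that the criticality outcome has no sham control; the documents do not support that. Nor do they say that a pre-post result will be claimed alone, so the rates in step 2 are conditional and are not the trial's error rate. Because 9.4.1 requires correction for multiplicity, the corrected rows are the ones to weigh.

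The reply to the second part is that Section 3 and 6.1.1 predict one direction per protocol. That holds for signed measures, so it would be wrong to infer that every criticality marker cancels. It does not rescue long-range temporal correlations, where Section 3 conflicts with 9.1 and 6.1.1.

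It is also fair that the interaction is a test 9.2 did not size, that its power after correction is modest, and that the simulation treats functional E/I as independent of the marker although 6.1.1 links them. These points limit what the term can deliver. They do not supply the missing baseline term. The effect correlations in 9.4.2 relate stimulation effects to one another, not to baseline, and subgroup analyses are marked as not applicable.

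**Conclusion.** The point holds as an inconsistent comparator, an unranked uncontrolled test and a mismatch between hypothesis and model. It is not a missing sham control. It should be corrected before unblinding, but it does not invalidate the primary analysis.

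The textual part is certain. The false-positive part depends on a pre-post result being claimed alone and on assumed drift: at 0.1 to 0.3 SD it ranges from under 1% to 35% after Bonferroni, depending on how many tests are counted. The power part rests on assumed opposite effects, baseline mix and reliability. It applies to long-range temporal correlations and other distance-from-criticality markers. There the planned average contrast can have little power for the effect that 9.1 describes.

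**What to change.** 1. Add the sham comparison to the criticality sentence in 9.1 and to the first row of Section 3, to match the synopsis.
2. In 9.4.1 and 9.4.2, state that for the resting EEG outcomes the confirmatory contrast is active versus sham, separately for cTBS and for iTBS, within participant. Adjust it for that session's pre-stimulation value beside sex, age and session order. Label within-condition pre-post t-tests descriptive.
3. Reconcile Section 3 with 9.1 and 6.1.1 on the predicted direction for long-range temporal correlations. For the distance-from-criticality markers, add a condition-by-baseline term with its main effect, where baseline is pre-stimulation functional E/I defined in advance (for example the three-session average assumed above). Test it against sham, include it in the multiplicity correction, and report the average contrast beside it.

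**Cost.** No new data: 9.1 and 9.4.8 already use pre-stimulation values, and 8.1 records EEG throughout each stimulation session. The model spends one or two degrees of freedom. The pre-stimulation covariate is a precision gain only: it cuts variance by about r², and costs about 2% if r = 0. The interaction is an extra test that 9.2 did not size. Its power is modest after correction, and lower than that of the average contrast if nearly all participants share one baseline regime.
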